#### c. Study Conditions:

- i. **Happify:** Participants assigned to the experimental condition will be sent a link to download the Happify Teens platform, as well as instructions on how to get started. These participants will have full access to the Happify for Teens platform for the entire 12-week study period. Happify for Teens has multiple tracks that target specific issues (e.g., “The Friendship Project”), which contain activity variants and games based on research in positive psychology, cognitive-behavioral therapy, mindfulness, etc.. Track activities are organized into five categories based on the acronym STAGER: savor (savoring and mindfulness), thank

(gratitude), aspire (goal-setting, reframing/optimism, and meaning), give (prosocial behavior, kindness, and forgiveness), empathize (perspective-taking and self-compassion), and revive (physical health). Although participants have access to all tracks on the Teens platform, four tracks related to stress and rumination will be featured: *Stress Buster 101, Stop the Worry Cycle, Be Kinder to Yourself, and Fight Those Negative Thoughts*. Participants will also have access to instant play activities. An example of an activity on Happify is called “Today’s grateful moment”, which asks participants to spend a few moments writing about something they are grateful for. They will not be told directly how often to engage with the platform; however, we will encourage them to engage with the platform regularly. Participants also will receive push notifications on their mobile device every other day to remind them to access the platform, and they will receive weekly emails as part of the Happify Health platform to help increase engagement. If a participant has not completed any activities within the platform for 7 days, they will also receive a text message or email (depending on their preferred mode of contact) from a member of the research team to check in. Participants will continue to have access to the Happify for Teens platform for an additional 4 weeks after the intervention period ends (until the 12-week assessment), but will receive no instructions, reminders or push notifications to use the platform during this time.

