3 ANALYSIS OBJECTIVES

The primary objective of this study is as follows:

- Comparing the Happify for Teens condition and the waitlist control groups, examine changes in perceived stress and rumination (brooding) across baseline, 4-weeks, 8-weeks (post-intervention), and 12-weeks.

The secondary objective of this study is as follows:

- Comparing the Happify for Teens condition and the waitlist control groups, examine changes in loneliness, optimism, and sleep disturbance across baseline, 4-weeks, 8-weeks (post-intervention), and 12-weeks.

The exploratory objectives of this study are follows:

- Determine the extent to which brooding mediates the relation between treatment condition (Happify for Teens vs. control) and perceived stress.
- Among those in the Happify for Teens treatment, we will explore the extent to which app usage (i.e., number of activities completed, number of active days) associates with each of the five outcome variables from the primary and secondary objectives.

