4 ANALYSIS SETS/POPULATIONS/SUBGROUPS

To be eligible for this study, the following criteria needed to be met:

- range in age from 13-17 years of age
- perceived stress scale (PSS) score greater than 14
- rumination-brooding subscale score of at least 10

We will create a subgroup of the treatment condition, stratified by those who did and did not average two activities completed per week. This threshold has been established in prior studies of the Happify app as a minimum needed for adults to benefit significantly from the program (e.g., Parks et al., 2018). We will examine descriptive statistics for these subgroups.

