6 HANDLING OF MISSING DATA AND OTHER DATA CONVENTIONS

Missingness will be evaluated using standard procedures when analyzing repeated measures data (van Buuren, 2018). First, missingness codes will be created that correspond with the variables in which data points are missing. A series of variables will be created that indicate missingness in each outcome at each measurement time point. We will then explore the extent to which various demographic markers and other variables in the dataset associate with missingness through a series of correlation tests. This practice will ultimately help us determine auxiliary variables for our models.

When working with missing data, there are two “gold standard” approaches to mitigating bias: multiple imputation and full information maximum likelihood (ML) estimation. However, as will be detailed below, multilevel modeling benefits from the fact that the approach does not assume that each group or cluster is balanced. In other words, even if individual A only has a baseline, but individual B has all four observations, no assumptions are violated, and the model will be unbiased (Raudenbush & Bryk, 2002). Thus, multilevel modeling allows us to avoid using a traditional missing data approach by simply harnessing the model’s extant capabilities. Given that we do not anticipate any significant missing data in the predictors or covariates, we plan to use restricted maximum likelihood (REML) estimation in the multilevel framework to account for missing outcome variable data. Final models will be run with identified auxiliary variables included as covariates.

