7.3 ADDITIONAL STATISTICAL MODELS

¹ MLM goes by many aliases in the social and behavioral science literature, including but not limited to: hierarchical linear modeling (HLM), linear mixed effects modeling, mixed modeling, and random effects modeling. Though some of these terms denote slight distinctions by subfield, each is more or less the same. I will use multilevel modeling, or MLM, throughout my documentation.

As noted in the published protocol paper, we will also examine brooding as a mediator of the relation between treatment condition and stress. We will harness a path modeling approach. In this path model, we will lag the effect such that treatment associates with 4-week stress, mediated by baseline brooding, and so on (see Figure 1). Path modeling will be completed using the *lavaan* package in R (Rosseel, 2012). Mediation effects will be calculated using bootstrapped 95% confidence intervals.

[figure not shown]

Figure 1. The proposed path model that will allow us to explore the extent to which brooding mediates the relation between treatment and perceived stress (PSS). Subscripts indicate each time point (B = Baseline; 4, 8, 12 = 4-, 8-, and 12-weeks, respectively). Single-headed arrows connecting two variables indicate regression pathways. Two-headed arrows indicate covariance. Single-headed arrows on a single box denote unmeasured endogenous variance.

We will also explore the relation between app usage and each outcome through a series of MLMs. The MLM parameters will be similar to the primary model (described previously). One MLM will be run for each primary and secondary outcome (brooding, perceived stress, loneliness, optimism, sleep disturbance), predicted by app usage. We will define the usage variable as: (Number of activities completed) / (Total number of days active on the app). This approach accounts for how involved participants were with the treatment while controlling for continued usage. We will parse usage into between- and within-person effects (see Carpenter et al., 2016). Between-person usage will be a Level-2 variable, indicating each participant's usage over the entire number of active days in the study, whereas within-person usage will be at Level-1, indicating the amount of app usage (relative to days active) between assessments.

NCT 0456788 – Statistical Analysis Plan

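### The five exploratory usage models in SAP 7.3 use activities per active day, which is neither usage measure in SAP section 3, does not reliably rank total use, and is undefined at zero use

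*SAP*

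**What the plan says.** The exploratory objective in SAP section 3 is to see how far "app usage (i.e., number of activities completed, number of active days) associates with each of the five outcome variables". That is two counts. Protocol I.d hypothesises that teens who do more activities improve more. Protocol II.e.I regresses each outcome, in the intervention arm, on the activity count with the baseline score as a covariate.

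SAP 7.3 then fixes a different predictor: "We will define the usage variable as: (Number of activities completed) / (Total number of days active on the app"). Its stated reason is: "This approach accounts for how involved participants were with the treatment while controlling for continued usage". One model is planned per outcome, so there are five. The ratio is split into a between-person part, taken over all active days, and a within-person part "indicating the amount of app usage (relative to days active) between assessments". No other usage term is described.

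Elsewhere the SAP measures use against calendar time. Section 4 forms a subgroup "stratified by those who did and did not average two activities completed per week", for descriptive statistics only. The dose-response curve at the end of SAP 7.3 relates each of the five outcomes to total activities divided by weeks enrolled.

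On missing data, SAP section 6 relies on the mixed model for missing outcomes and begins its choice of REML with "Given that we do not anticipate any significant missing data in the predictors or covariates". Protocol II.c.i provides a staff check-in ("If a participant has not completed any activities within the platform for 7 days"). It also says that participants keep access in weeks 8 to 12 "but will receive no instructions, reminders or push notifications to use the platform during this time".

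**The concern.** The objective asks about the amount of use, and the models measure how much is done on a day when the app is opened. Dividing by active days takes duration out of the predictor. It does not adjust for duration as a separate covariate would: on the log scale, log(A/D) = log A − log D, so the two counts are forced to have equal and opposite coefficients.

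Two things are at stake. First, a null or a positive result from these five models could be reported as a test of whether more use goes with more improvement, when it is about intensity on days of use. Second, a person or interval with no active days has no value. If such values are left missing, the lowest-use records leave the five models, and they are the low end of the relation being studied.

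**Working it through.** The documents give no usage distribution and no figure for this variable, so there is nothing to reproduce. The users below are hypothetical. They test what the definition can and cannot distinguish.

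Inputs: A = activities completed and D = active days (both collected, protocol II.b.i); ratio A/D (SAP 7.3); 12-week study period (protocol II.d); threshold of two activities per week (SAP section 4); 400 participants planned in the intervention arm (protocol, Sample Size).

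**Between persons.** Compare A/D with A/12, the activities per week over 12 weeks.

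| A | D | A/D | A/12 | Averages two per week? |
|---|---|---|---|---|
| 2 | 1 | 2.0 | 0.17 | no |
| 112 | 56 | 2.0 | 9.33 | yes |
| 24 | 24 | 1.0 | 2.00 | yes |
| 3 | 1 | 3.0 | 0.25 | no |
| 100 | 50 | 2.0 | 8.33 | yes |
| 0 | 0 | 0/0 | 0 | no |

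Rows 1 and 2 tie, although total activities differ by 112/2 = 56-fold. Rows 1 and 3 are in reverse order relative to the SAP's own threshold. Rows 4 and 5 are also reversed.

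**Within a person.** Take 20 activities on 10 days in weeks 0–4, 4 on 2 days in weeks 4–8, and 2 on 1 day in weeks 8–12.

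- Ratio: 20/10 = 4/2 = 2/1 = 2.0, so every deviation from the person's mean is 0.
- Fall in activities: 1 − 2/20 = 90%.
- Activity count: mean (20 + 4 + 2)/3 = 8.67; deviations +11.33, −4.67, −6.67.
- If weeks 8–12 are empty (20, 4, 0 activities on 10, 2, 0 days), the ratio is 2.0, 2.0, 0/0. The count has mean 8 and deviations +12, −4, −8.

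**Is the ratio unrelated to total use?** Assume lognormal intensity and active days with log-SDs s_r and s_d and log-scale correlation ρ. Then

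corr(log ratio, log total) = (s_r + ρ·s_d) / √(s_r² + s_d² + 2ρ·s_r·s_d).

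- s_r = 0.3, s_d = 1.0, ρ = −0.5: −0.20/√0.79 = −0.23.
- s_r = 0.5, s_d = 0.5, ρ = 0.5: 0.75/√0.75 = 0.87.
- With ρ = 0, the settings tried gave 0.29 to 0.71.

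These settings are assumptions, and a simulation agreed with the formula. The ratio usually carries some information on total use, but not enough to stand in for it.

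**Zero use.** The rate is not in the documents. Each 1% of 400 with no use at all is 4 people, and up to 4 × 3 = 12 of 400 × 3 = 1,200 scheduled week 4, 8 and 12 records per outcome. An assumed 5% to 30% would be 20 to 120 people. Empty intervals among people who did use the app would add to the records affected.

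**The case against.** The strongest reply is that amount of use is already analysed. The dose-response curve covers all five outcomes. For anyone enrolled the full 12 weeks its predictor is the protocol's count divided by a constant, and a non-user scores 0/12 = 0. This stands: non-users are not lost from every usage analysis, and the hypothesis that more activities bring more improvement has a planned analysis. What the curve does not supply is any analysis of active days or any within-person effect of amount of use.

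A second reply is that the ratio is deliberate, is built from both section 3 counts, and addresses a legitimate exploratory question. That also stands, as a reason to keep it as an added measure. It does not remove the mismatch between the objective and the only usage predictor in the five models.

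A third reply is that the evidence for empty intervals is thin. A check-in after 7 days foresees a week without activities, not a blank four weeks, and stopping reminders does not mean that use stops. The SAP also does not say that undefined values would be left missing, and the study it cites for the between/within split cannot be checked here. All of this is fair. It limits what can be said about frequency, but the plan still has no rule.

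From the ties and reversals a reader might infer that the ratio carries no information on total use. The documents do not support that. Its numerator is total activities, and under the assumptions above the correlation with total use ranges from slightly negative to strongly positive. The examples are chosen cases that show what the ratio can fail to separate, not how users will typically fall.

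**Conclusion.** The five usage models, as written, do not answer the usage objective in SAP section 3 and do not use the protocol's predictor. They estimate associations with intensity per active day. That measure can tie users whose activities differ 56-fold, can reverse users across the SAP's own threshold, and can stay constant through a 90% fall in use. It is undefined at zero active days, with no rule, and the term active day is not defined.

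The definition, the mismatch and the arithmetic come directly from the text. The number of records affected by 0/0 is unknown, and their loss from these models depends on undefined values being left missing.

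The consequence is limited. The models are exploratory and non-randomised, overall dose is covered by the dose-response curve, and the randomised comparison is unaffected. The change is still worth making because it is specific and cheap, and nothing else in the SAP covers active days or within-person amount of use.

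**What to change.** In SAP 7.3:

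- Use the number of activities completed as the usage predictor, and the number of active days in a separate model. Split each into a between-person part and a within-person part based on the intervals between assessments.
- Code zero use as 0 and define an active day.
- Say how the baseline record is treated, since no interval of use precedes it.
- Keep the ratio, if wanted, as a secondary intensity measure limited to people and intervals with at least one active day.
- Report all of these as non-randomised associations.

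The cost is SAP wording only, because protocol II.b.i already collects both counts. The downsides are up to ten exploratory models instead of five (two counts × five outcomes), and counts that may be skewed.
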